3.3 Exploratory Effectiveness Endpoint

The exploratory effectiveness endpoints are defined as:

- Incidence of resection
- Histology of duodenal tissues when resection is performed
- Incidence of acute (within 3 months) and late (>3 months) duodenal toxicity (for unresected subjects)
- Theoretical dose escalation from post-TraceIT treatment plan
- TraceIT persistence (at 6-months post-TraceIT in nonresected subjects)
- Change from baseline in EORTC QoL (QLQ-C30) and QLQ-PAN26
- Comparability of visualization of the fiducial marker and TraceIT hydrogel using a standardized visualization score
- Progression free and overall survival through follow-up

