3.3.1 Statistical Methods

The proportion of resected subjects in the MITT or PP population, localized (resectable, BRPC or LAPC) subgroup may be calculated with an exact (Clopper-Pearson) 95% confidence interval for the true proportion, when appropriate.

The incidence of acute (within 3 months) and late (>3 months) duodenal toxicity for unresected subjects will be reported by CTCAE grade and timing.

Histology of duodenal tissue (Duodenum Damage Score) will be summarized for those subjects when resection is performed.

The summary of theoretical dose escalation from post-TraceIT treatment plan, and , migration and stability at 2-6 weeks post-TraceIT, TraceIT persistence at 6-months post-TraceIT in non-resected subjects will be presented in separated table. The pre-TraceIT and post-TraceIT duodenal space measured by site during index procedure and/or by independent assessors will be summarized separately. Average duodenal space will be

calculated if the measurements were taken from multiple observation points or duplication.

The EORTC QLQ-C30 is a questionnaire developed to assess the quality of life of cancer patients. The pancreatic cancer module QLQ-PAN26 is intended for patients at all disease stages undergoing surgical resection, palliative surgical intervention, endoscopic palliation or palliative chemotherapy. Changes in Quality of Life Measures as assessed overall and subdomains (scales) of the EORTC-QLQ-C30 and QLQ-PAN26 will be evaluated.

The five functional scales (physical, role, emotional, cognitive and social), three symptom scales (fatigue, nausea & vomiting and pain), a global health status/QOL scale, and six single items (dyspnea, insomnia, appetite loss, constipation, diarrhea and financial difficulties) from EORTC-QLQ-C30 will be summarized according EORTC QLQ-C30 Scoring Manual third edition.

The fifteen symptom items and two functional scales from QLQ-PAN26 will be analyzed according EORTC QLQ-PAN26 Scoring Manual 2.2.

Those analysis will be repeated by localized (resectable, BRPC and LAPC), as well as resected and unresected subgroup, if applicable. Scores will be compared to baseline using either a paired t-test or Wilcoxon Signed-Rank test when appropriate.

The result of comparability of visualization of the fiducial marker and TraceIT hydrogel will be summarized using a standardized visualization score for all subjects injected with TraceIT Tissue Spacer.

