3.4 Safety Endpoint

Any adverse event (AE) occurred Procedure through 18-month visit will be recorded and listed. All collected AEs will be recorded by body system and preferred term in accordance with NCI Common Terminology Criteria for Adverse Events (CTCAE) v4.0 (NCI, Oct 2009) for severity and/or MedDRA term.

The safety endpoint for this study is defined as “TraceIT administration procedure-related events which result in a delay in initiation of RT” as reviewed and adjudicated by a Clinical Events Committee.

The timing (month) of AE will be categorized as <=3 months, >3 to <=6 months, >6 to <=12 months, >12 to <=18 months, by its value calculated as:

(Date of AE started - Date of index procedure + 1) / (365.25/12) and rounded to 2 decimal places.

SADE is defined as a serious adverse event that is believed to have been caused by or is associated with the device. UADE is defined as any serious adverse effect on health or safety, or any life-threatening problem or death caused by, or associated with, a device if that effect, problem or death was not previously identified in nature, severity or degree of incidence in the Investigational Plan, or any other unanticipated serious problem associated with a device that relates to the rights, safety or welfare of subjects. SADEs and UADEs will be investigated immediately once occurred and if the sponsor determines that unreasonable risk to subjects is possible, the study will be terminated.

To standardize the reporting, a Clinical Events Committee (CEC) was convened at the beginning of the study to provide:

- Continuous review and validation of all adverse events that occur over the course of the study and the subsequent classification of these adverse events as related to the device or procedure.
- Oversight for issues affecting general subject welfare, including recommendations on changes to the protocol or device and if appropriate recommendation concerning early study termination if new information is learned that would affect the risk/benefit analysis presented within this clinical investigational plan.

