3.4.1 Statistical Methods

CEC adjudicated AEs will be summarized by term, by term and procedure/device relationship, and by terms and severity (CTCAE Grade). In addition to the general presentation of safety events, the following will be calculated and reported:

- The number and percentage of subjects who experienced TraceIT administration procedure-related events which result in a delay in initiation of RT
- The number and percentage of subjects with at least one duodenal adverse event presented by grade and timing; i.e., acute (within 3 months) and late (>3 months). A similar presentation will be provided for non-resected subjects only.

Additionally, the numbers and percentages will be calculated for subjects who have developed one or more following events: AEs, SAEs, UADE, SADE, procedure related

AEs, device related AEs, radiation therapy related AEs, duodenal related AEs by site and total.

Adverse event overall listing will include AE CTCAE term, AE CTCAE SOC, onset days since procedure and duration, AE attribution, CTCAE grade and adjudication term, SAE and classification, UADE, action taken, outcome and residual effects.

Single imputation will be implemented for partial start/end dates (missing month and/or day) of adverse events, or concomitant medications.

For the missing start date:

- Only the start day is missing: the 15th day of the month will be used if the resulted imputed date is after the index procedure date; otherwise the procedure date will be used.
- Both the start day and the start month are missing: the 15th day of January will be used if the resulted imputed date is after the index procedure date; otherwise the procedure date will be used.

For the missing end date:

- If the end day is missing, the 15th day of the month will be used if the resulted imputed date is after the corresponding start date; otherwise the last day of the month will be used.
- If end day and end month are both missing, the 15th day of December will be used if the resulted date is after the corresponding start date; otherwise the 31st day of December will be used.

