4.1.2 Modified Intent-To-Treat Population (MITT)

All subjects enrolled in the study and who are a Technical Success will be included in the Modified Intent-to-Treat population. This will be the primary analysis population for purposes of non-safety outcome data.

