4.1.5 Safety Population (SAF)

The Safety Population is defined to be all subjects for whom TraceIT administration is attempted (whether or not administration was successful). For the purposes of this study, the Safety Population is the same as the ITT Population.

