5 ADDITIONAL DATA ANALYSES

5.1 Other Endpoints/Measurements

5.1.1 Subject Disposition

The number and percentage of ITT, MITT, PP and SAF population will be summarized. Subjects who passed pre-screening will be consented for the study and will undergo a secondary screening. The number of subjects who consented, screening failed and early terminated prior index procedure (TraceIT administration isn't attempted) will be presented. The number and percentage of non-injection TraceIT subjects will be presented along with the reason they were not able to be injected. The number and percentage of treated subjects who do not complete the study will be presented, along with the reason for early termination/withdrawal. Subject accountability by investigative site and by study visit will also be presented.

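### The last AE timing bin closes before the Month 18 visit window does, and the late duodenal percentage has no at-risk denominator

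*SAP*

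**What the plan says.** **Clock and bins.** SAP 3.4 measures AE timing from the index procedure, as "Date of AE started - Date of index procedure + 1) / (365.25/12) and rounded to 2 decimal places". It names four categories: up to 3 months, over 3 to 6, over 6 to 12, and over 12 to 18. No later or open-ended category follows.

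**Collection period.** SAP 3.4 and protocol 9.1.1 both collect AEs up to the 18-month visit. Protocol 6.4.15 gives that visit a window of 28 days either side.

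**Duodenal tables.** SAP 3.4.1 asks for the number and percentage of subjects with a duodenal AE, by grade and by timing, split as "acute (within 3 months) and late (>3 months"), and for the same display in non-resected subjects. It names no time origin, denominator or analysis set. SAP 3.3 also lists this toxicity among the exploratory endpoints: "Incidence of acute (within 3 months) and late (>3 months) duodenal toxicity (for unresected subjects").

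**Populations.** The Safety Population (SAP 4.1.5) is "all subjects for whom TraceIT administration is attempted (whether or not administration was successful"). For MITT, SAP 4.1.2 says "This will be the primary analysis population for purposes of non-safety outcome data".

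**Non-injection subjects.** Protocol 6.4.5.1 keeps in the safety analysis a subject whose duodenum was punctured but who received no hydrogel. Protocol 6.4.7 and Table 3 end that subject's schedule at 30 days (+7), or later if an AE has still to resolve or stabilize.

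**The concern.** Two rules do not match the data they are meant to summarize.

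(a) A bin with a fixed upper edge is applied to a collection period that ends at a visit. If the visit falls late in its window, or in many cases on its exact due date, a correctly collected event fits none of the four categories. The programmer would have to drop it from the summary or improvise.

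(b) A percentage of subjects with a late event is informative only if the denominator holds subjects who could have been seen to have one. A non-injection subject who leaves the schedule at about one month adds to the denominator and, absent an ongoing AE, cannot add to the numerator. The same applies to anyone who withdraws before 3 months, since protocol 6.4.2 keeps withdrawn treated subjects in the safety analysis. The effect is to lower the late rate and make a zero count look more reassuring than the observation supports. With about six subjects, one such person visibly moves the figure.

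**Working it through.** There is no sample-size or power figure to reproduce. The check applies the SAP's own timing formula to day offsets d after the index procedure.

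**Formula (SAP 3.4).** month = (d + 1) / (365.25/12) = (d + 1) / 30.4375, rounded to 2 decimals.

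**Bin edges**
- d = 90: 91/30.4375 = 2.99, the last day up to 3 months
- d = 91: 92/30.4375 = 3.02, the first late day
- d = 547: 548/30.4375 = 18.00, the last day in the final bin
- d = 548: 549/30.4375 = 18.04, no bin

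Rounding moves the upper edge by only one day (548/30.4375 is 18.004 unrounded), so it is not the cause.

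**Month 18 visit.** For every index date from 2018 to 2021, 18 calendar months is 546 to 550 days. The due date is therefore already past the bin on days 548 to 550, which is about 58% of those index dates. Adding the 28-day allowance:
- 546 + 28 = 574, value 575/30.4375 = 18.89; unbinned days 574 − 547 = 27
- 550 + 28 = 578, value 579/30.4375 = 19.02; unbinned days 578 − 547 = 31

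So 27 to 31 days of in-window collection have no category.

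**Late denominator.** Scheduled non-injection follow-up ends by day 30 + 7 = 37, value 38/30.4375 = 1.25 months. Late opens on day 91, which is 91 − 37 = 54 days later.

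The documents give no non-injection rate, so the following mix is an assumption: six subjects in the Safety Population, one of them not injected.

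| Late events | Safety Population, n = 6 | Followed past 3 months, n = 5 |
|---|---|---|
| 1 | 1/6 = 16.7% (exact 95% CI 0.4 to 64.1) | 1/5 = 20.0% (0.5 to 71.6) |
| 0 | upper limit 1 − 0.025^(1/6) = 45.9% | upper limit 1 − 0.025^(1/5) = 52.2% |

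SAP 3.4.1 plans no interval here. The table uses the Clopper-Pearson method that the SAP names for technical success, to show what a reader could infer.

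**Non-resected table.** Table 3 has no resection visit, and neither document says how a non-injection subject's resection status is set. If such a subject were counted as non-resected, with two others resected (assumed), one late event would read 1/4 = 25.0% instead of 1/3 = 33.3%.

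**The case against.** The strongest reply is that little depends on either point. The output is descriptive, no threshold uses it, and SAP 5.1.1 already reports non-injection subjects with reasons and adds: "Subject accountability by investigative site and by study visit will also be presented". A careful reader could work out 1/5 for themselves. That limits the importance but does not answer the point. Visit attendance does not give the number observed past day 90, because the Month 3 window of 14 days either side runs over roughly days 77 to 105. It is also fair to say that a non-injection subject with an ongoing AE may be followed longer, and that the proposed denominator does not equalize exposure: a subject seen to day 91 counts the same as one seen to Month 18.

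A reader might infer more than the documents support:
- *The index clock is wrong and radiotherapy timing is needed.* The clock suits a device study. The protocol's events committee classifies events by relation to radiotherapy (9.1.2), and SAP 3.4.1 counts radiotherapy-related AEs. The listing gives "onset days since procedure and duration" without radiotherapy dates, which is an inconvenience and not an error.
- *Late duodenal events are lost at 18 months.* They are not. The late category has no upper limit, and events past day 547 are still listed. Only the four-bin summary is affected.
- *The analysis set is undefined.* The general rules largely settle it: Safety Population for safety tables, MITT for non-safety outcomes. What is missing is a sentence tying the 3.4.1 tables to the former.
- *Resected subjects distort the late rate unchecked.* The non-resected companion table largely deals with this, and SAP 3.3.1 has the same restriction: "The incidence of acute (within 3 months) and late (>3 months) duodenal toxicity for unresected subjects will be reported by CTCAE grade and timing".

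**Conclusion.** Both points hold, and both are minor. The bin mismatch is arithmetic on the SAP's own rule: the last category ends at index day 547, collection can run to day 574 to 578, and 27 to 31 days have no category. It rests only on reading Month 18 as 18 calendar months.

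The denominator point rests on one inference, that the 3.4.1 tables default to the Safety Population, and matters only if at least one subject is not injected or leaves before 3 months. In the assumed case of one in six, the late percentage moves from 20.0% to 16.7%, and the exact upper limit for zero events from 52.2% to 45.9%. The direction is downward whenever an unobservable subject is counted. Error rates, power and the study's defined safety endpoint, radiotherapy delay, are not touched.

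**What to change.** Change the SAP text as follows.

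1. SAP 3.4: replace the last category with *over 12 months through the 18-month visit*.
2. SAP 3.3.1 and 3.4.1: state that acute and late are timed from the index procedure. In 3.4.1, state that the tables use the Safety Population.
3. SAP 3.4.1: give the late percentage over subjects still followed beyond 3 months, and print that n. Keep the non-resected table, and leave out of its late column anyone not followed past 3 months.

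Optionally, add days since the first and last radiotherapy fraction to the AE listing, so that a reader can re-time an event without joining listings. A separate table timed from radiotherapy is not needed.

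The cost is a few sentences and no new data collection for items 1 to 3. The downside is a smaller late denominator, and so a coarser percentage, in a study that is already very small.

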3.4.1 Statistical Methods

CEC adjudicated AEs will be summarized by term, by term and procedure/device relationship, and by terms and severity (CTCAE Grade). In addition to the general presentation of safety events, the following will be calculated and reported:

- The number and percentage of subjects who experienced TraceIT administration procedure-related events which result in a delay in initiation of RT
- The number and percentage of subjects with at least one duodenal adverse event presented by grade and timing; i.e., acute (within 3 months) and late (>3 months). A similar presentation will be provided for non-resected subjects only.

Additionally, the numbers and percentages will be calculated for subjects who have developed one or more following events: AEs, SAEs, UADE, SADE, procedure related

AEs, device related AEs, radiation therapy related AEs, duodenal related AEs by site and total.

Adverse event overall listing will include AE CTCAE term, AE CTCAE SOC, onset days since procedure and duration, AE attribution, CTCAE grade and adjudication term, SAE and classification, UADE, action taken, outcome and residual effects.

Single imputation will be implemented for partial start/end dates (missing month and/or day) of adverse events, or concomitant medications.

For the missing start date:

- Only the start day is missing: the 15th day of the month will be used if the resulted imputed date is after the index procedure date; otherwise the procedure date will be used.
- Both the start day and the start month are missing: the 15th day of January will be used if the resulted imputed date is after the index procedure date; otherwise the procedure date will be used.

For the missing end date:

- If the end day is missing, the 15th day of the month will be used if the resulted imputed date is after the corresponding start date; otherwise the last day of the month will be used.
- If end day and end month are both missing, the 15th day of December will be used if the resulted date is after the corresponding start date; otherwise the 31st day of December will be used.

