Screening/Baseline: (within 45 days prior to planned TraceIT hydrogel injection)	
Subjects who appear to meet the eligibility criteria will be consented for the study and will undergo screening. Information to be collected at screening and baseline includes:
 
 • Demographic information: date of birth, weight and height, race • Disease documentation: tumor location, initial resectability status, tumor staging, largest pre-treatment dimension of tumor (cm) • Medical/Surgical History/Current status: concomitant medical conditions, prior medical conditions, prior surgeries, prior therapies (e.g., induction chemotherapy) • Physical Examination: including sitting blood pressure, pulse, temperature, weight, anticoagulation status, Zubrod Performance Score • Laboratory testing for hematology plus platelets, creatinine, AST/ALT and bilirubin and baseline serum carbohydrate antigen (CA) 19-9 • Pregnancy test for women of child-bearing potential. • EORTC-QLQ-C30 and QLQ-PAN26 • Assessment of baseline duodenal symptoms per NCI CTCAE • Baseline concomitant medications

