6.4.10 Final RT Fraction

The following assessments are to be performed at the final RT fraction:

- Physical Assessment (including vital signs, weight and Zubrod performance score)
- EORTC-QLQ-C30 and QLQ-PAN26
- Assessment of duodenal focused Adverse Events documented using NCI CTCAE
- Other Adverse Events per NCI CTCAE
- Changes in concomitant medications used to treat intestinal symptoms

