9 ADVERSE EVENTS

9.1 Definitions

Adverse Event (AE): Any untoward medical occurrence in a subject that is of new onset or has become worse including consequences of medical therapy resulting from a potential study-related delay in radiation treatment

Adverse events are to be recorded from initiation of fiducial marker placement through the 18 month visit.

Adverse Device Effect (ADE): An adverse event that is believed to have been caused by or is associated with the device.

Serious Adverse Event (SAE): An adverse event that:

- a. Led to death
- b. Resulted in a life-threatening illness or injury
- c. Resulted in a permanent impairment of a body structure or a body function
- d. Resulted in in-patient hospitalization or prolongation of existing hospitalization
- e. Resulted in medical or surgical intervention to prevent permanent impairment to body structure or a body function

The investigator will report serious events to the Sponsor and to his/her IRB per the institution's requirements and as specified in section 8.1.1.

Serious Adverse Device Effect (SADE): A serious adverse event that is believed to have been caused by or is associated with the device.

Unanticipated Adverse Device Effect (UADE): Any serious adverse effect on health or safety, or any life-threatening problem or death caused by, or associated with, a device if that effect, problem or death was not previously identified in nature, severity or degree of incidence in the Investigational Plan, or any other unanticipated serious problem associated with a device that relates to the rights, safety or welfare of subjects.

Event Severity: Event severity will be graded in accordance with the guidelines provided in the NCI Common Terminology Criteria for Adverse Events (CTCAE) v 4.0 (NCI, Oct. 2009). For those events that do not have a term identified in the CTCAE, events should be identified using the following criteria:

Mild: Event causes a low level of inconvenience or discomfort, does not interfere with subject's usual activities, and is usually transient; treatment not ordinarily needed for relief of symptoms.

Moderate: Event causes moderate level of inconvenience or discomfort, may interfere with subject's usual activities; new treatment or change in treatment for symptoms may be needed.

Severe/Serious: Event causes severe discomfort and considerable interference with subject's usual activity and requires treatment and/or hospitalization.

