3 ENDPOINT ANALYSIS

All data collected in this study will be documented using summary tables and subject data listings. Continuous variables will be summarized using descriptive statistics, specifically the mean, median, standard deviation, minimum and maximum, when appropriate.

Categorical variables will be summarized by frequencies and percentages.

Changes from baseline in dosimetric parameters and quality of life parameters will be assessed using a paired t-test or, if not normally distributed, the nonparametric Wilcoxon Signed-Rank test for continuous variables and Chi-Square and/or McNemar's test for dichotomous variables.

Nominal p-values associated with statistical tests will be reported, but no significance level will be applied to the values. No adjustments to nominal p-values are planned since this is a hypothesis-generating study.

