5.1.5 Concomitant Medication

Numbers and percentages of subjects in the ITT population with any medication changes to treat intestinal symptoms will be summarized by the timing of start administration.

The timing of concomitant medication will be categorized as prior index procedure date, from index procedure date up to 3 months post-procedure, after 3 months post-procedure. The month interval between index procedure and medication administration is calculated as:

(Date of medication started - Date of index procedure + 1) / (365.25/12) and rounded to 2 decimal places.

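### Partly dated medications that began before the procedure are tabulated as starting on the procedure date

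*SAP*

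**What the plan says.** SAP 3.4.1, in the safety methods, sets the scope of the rule: "Single imputation will be implemented for partial start/end dates (missing month and/or day) of adverse events, or concomitant medications". One start-date rule then serves both record types. If only the day is missing, the 15th of the recorded month is used when it falls after the index procedure, and the procedure date otherwise. If day and month are both missing, it reads: "15th day of January will be used if the resulted imputed date is after the index procedure date; otherwise the procedure date will be used".

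SAP 5.1.5 describes the table that uses medication start dates. It counts "subjects in the ITT population with any medication changes to treat intestinal symptoms will be summarized by the timing of start administration". Timing is "categorized as prior index procedure date, from index procedure date up to 3 months post-procedure", with a third category for starts after 3 months. The interval is start date minus index date plus 1, divided by 365.25/12 and rounded to two decimals.

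The Protocol collects the two record types over different periods. Section 9.1 states: "Adverse events are to be recorded from initiation of fiducial marker placement through the 18 month visit". Medications are also taken at screening: "Baseline concomitant medications" is an item in the Protocol Summary and again in section 6.4.4. Later visits, such as the final RT fraction (6.4.10), collect "Changes in concomitant medications used to treat intestinal symptoms". Neither document gives medications a separate partial-date rule.

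**The concern.** The rule asks only whether the mid-month or mid-January date falls after the procedure. It never asks whether the recorded month or year already places the start before it. For an adverse event this does no harm, because events are recorded only from fiducial placement, which is part of the index procedure. For a medication it can override what the site wrote down. A drug recorded as starting in an earlier month or year is moved forward to the procedure date, so it cannot reach the pre-procedure category that SAP 5.1.5 provides.

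At stake is the reading of one descriptive table. A drug for intestinal symptoms that was started before TraceIT would appear as a start on the day of the procedure. With about six subjects, a single such record shows in the percentages.

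**Working it through.** The plan gives no figure to reproduce here, so the check applies the written rule and formula to partial dates. All calendar dates are illustrative assumptions; the result follows from the rule itself.

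**Inputs.** The start-date rule is from SAP 3.4.1. The timing formula and categories are from SAP 5.1.5; one month is 365.25/12 = 30.4375 days. The planned sample of six subjects is in SAP 3.1.2.

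**Step 1: the rule as written, index procedure 10 June 2019**

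| Recorded start | Imputed start | Months | SAP 5.1.5 category |
|---|---|---|---|
| March 2018 | 10 June 2019 | (0 + 1)/30.4375 = 0.03 | up to 3 months |
| 2018 only | 10 June 2019 | 0.03 | up to 3 months |
| May 2019 | 10 June 2019 | 0.03 | up to 3 months |
| 2019 only | 10 June 2019 | 0.03 | up to 3 months |
| June 2019 | 15 June 2019 | (5 + 1)/30.4375 = 0.20 | up to 3 months |

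The first three starts are plainly before the procedure and are misclassified. The last two are truly ambiguous.

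**Step 2: does this depend on the index date?** The rule was run for every index date from 1 January 2018 to 31 December 2020 (1,096 dates), with recorded years 2015 to 2022 (8) and the month either missing or one of 12 (13 options). That is 1,096 × 8 × 13 = 113,984 partial dates.

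- None of the 113,984 reaches the pre-procedure category.
- In 63,057 of them the recorded month or year is plainly before the procedure. All 63,057 fall in the category up to 3 months.
- These counts describe the rule, not the trial's data.

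**Step 3: dates in the procedure's own month or year.** The imputed start is at most 14 days after the index date, so the timing runs from 0.03 to (14 + 1)/30.4375 = 0.49 months. These dates also always fall in the category up to 3 months.

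**Step 4: a sign that the floor was written for adverse events.** Take a drug recorded from March 2018 to April 2018, with the same index date. Its start becomes 10 June 2019. Under the end-date rule in SAP 3.4.1, 15 April 2018 is not after that start, so the last day of the month is used: 30 April 2018. The drug then ends before it starts.

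**Step 5: size in the table.** One subject is 100/6 = 16.7 points of a row. If subjects are replaced, as Protocol 6.5 allows, it would be 100/7 = 14.3 with seven ITT subjects or 100/8 = 12.5 with eight.

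**Step 6: the corrected rule.** When the known year, or year and month, is allowed to decide first, all 63,057 plainly earlier dates become pre-procedure starts. Later dates do not change. For example, a restart recorded as September 2019 is imputed to 15 September 2019, 97 days after 10 June. Its timing is (97 + 1)/30.4375 = 3.22 months, so it stays in the category after 3 months.

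**The case against.** The strongest reply concerns reach. The SAP 5.1.5 table covers changes in medication for intestinal symptoms, not all medications, and the Protocol separates baseline medications from later changes. A drug dated more than a year before the procedure may be an unchanged baseline drug that never enters the table. On that reading the exposed group is small: recent intestinal drugs, partly dated, in an earlier calendar month or year. This stands as a limit on the effect, because the documents do not settle how unchanged baseline drugs are handled. It does not remove the problem. The table classifies by start of administration and has a pre-procedure category, so some earlier starts must be expected.

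Other points also limit the effect:

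- Protocol 7.8 and SAP 3.1.3 expect little missing data, and there may be no partial medication dates at all.
- The error overstates intestinal drug starts after the procedure, so in this table it does not flatter the device.
- The 16.7 points is a ceiling. A subject who already has a correctly dated change within 3 months adds nothing to that row, although the pre-procedure row may still lose that subject.
- SAP 3 promises that "All data collected in this study will be documented using summary tables and subject data listings", so a reader may be able to check single records. The table itself would still be wrong.
- SAP 5.6 allows amendment before analysis, and SAP 7.3 leaves programming rules to code or footnotes. Correction is therefore easy, but the written rule is unchanged until it is made.

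Where the known parts match the procedure's own month or year, the floor is a cautious choice and not an error.

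**Conclusion.** The concern holds, as a minor one. For the two patterns that SAP 3.4.1 defines (day missing; day and month missing), a medication whose recorded month or year precedes the procedure is always dated to the procedure itself, so the pre-procedure category of SAP 5.1.5 is closed to it. Confidence in this reading is high, because it follows directly from the text.

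The practical effect is unknown and may be nil. It depends on whether any tabulated intestinal drug has a partial start date and on how unchanged baseline drugs are treated. Complete dates are unaffected. A missing month with a known day, and a wholly missing start date, have no rule in the SAP and are outside this conclusion. No primary, secondary or safety endpoint uses the table.

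**What to change.** Keep the procedure-date floor for adverse events. Give concomitant medications their own start-date rule in SAP 3.4.1:

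1. If the known year, or year and month, is before the procedure's, class the drug as started before the procedure. The category needs no imputed date.
2. If it is later than the procedure's, keep the existing rule (15th of the month, or 15 January).
3. If it matches the procedure's month or year, look at the baseline medication record for the same entry. A drug on that record with no later change or restart is classed as started before the procedure. Otherwise query the site.
4. If the record is still unresolved, apply the existing floor and mark it with a footnote.

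Step 1 corrects the error. Steps 3 and 4 deal with the ambiguous dates and assume that the case report form lets a baseline entry be matched to a later one, which the documents do not show.

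The cost is one SAP paragraph, a small programming change and possibly a few site queries. A few records may stay ambiguous, but they would be visible as such.
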